Parents/carers within the same family will be randomised to the same arm, making this a cluster RCT, given responses within the same family are potentially highly correlated. We might expect, based on our previous research with families, an average cluster size within families of up to a maximum of 1.5 parents and a high degree of correlation among parents/carers from the same family, so also allow for an ICC=0.5 (Davé et al., 2008). Following Teerenstra et al. (2012), we also allow for a correlation between baseline and follow-up measures of primary outcome of $r=0.5$ (this is a conservative estimate based on published SDQ test-retest correlations between 0.74-0.84; Nowak et al., 2008). The sample size is then inflated to account

for 20% of families being lost to follow-up at the 12-month post-randomisation follow-up time point.

Allowing for the above assumptions and an effect size to be detected of 0.35 with 90% power and a two-sided alpha of 0.05, a sample size of N=412 (N1 =206, N2=206) is required.

The choice of effect size was based on meta-analytic effects from similar parenting programmes' meta-analyses and on the basis that similar Triple P programmes report large effect sizes that are typically >0.5, some as large as 0.8. On this basis, we reduced to 0.35 given the unique nature of the population in this trial. Further evidence based on individually delivered teen parenting programmes was quite challenging to find well powered RCTs or meta-analyses, so meta-analyses that were slightly outside our age range were also considered.

An efficacy trial for standard teen Triple P report an effect of $d=0.62$ (Salari et al, 2014). In the other meta-analyses, it was also generally around $d=0.6$. Given that we are delivering this to a slightly different population, the current planned MDES 0.35 is justifiably conservative (mainly as most studies have been quite small and in a very different population). Considering the MDES from a clinically meaningful effect size, $d=0.35$ equates approximately to a 2-point change on our primary outcome, an effect smaller than this is unlikely to provide any meaningful change. With reference to sample size and secondary outcomes, the trial is currently powered on the basis of detecting an appropriate MDES for the primary outcome which is standard practice in all major trials (CONSORT statement; Schulz et al., 2010).

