All participants (in both trial arms) will complete assessments at baseline (prior to randomisation), 6- and 12-months post-randomisation and will be given a choice of how these are completed. These assessments can be completed in a number of ways, face-to-face, online on a website, via telephone, via videoconferencing, or on paper via the post. Participants, parents/guardians, young people and key stakeholders will be invited to participate in semi-structured interviews to ascertain acceptability and their experience of

the parenting programme and being in the trial. We will interview a sample of those randomised to each arm of the trial.

Randomisation

Families will be randomised with equal probability to either the intervention or comparator arm using random permuted blocks (block size 4), stratified by local authority site. The statistician doing the analysis will be blind to the treatment allocation. As the families and practitioners are not blind to treatment allocation (as this would be impossible given the intervention), there is no issue in terms of predictability.

Sample size

Sample size calculations were conducted using R version 4.1.2 (2021-11-01), and the 'pwr' R package.

Parents/carers within the same family will be randomised to the same arm, making this a cluster RCT, given responses within the same family are potentially highly correlated. We might expect, based on our previous research with families and consultation with the TMG (Trial Management Group), an average cluster size within families of up to a maximum of 1.5 parents and a high degree of correlation among parents/carers from the same family, so also allow for an ICC=0.5 (Davé et al., 2008). Following Teerenstra et al. (2012), we also allow for a correlation between baseline and follow-up measures of primary outcome of $r=0.5$ (this is a conservative estimate based on published SDQ test-retest correlations between 0.74-0.84; Nowak et al., 2008). The sample size is then inflated to account for 20% of families being lost to follow-up at the 12-month post-randomisation follow-up time point.

Allowing for the above assumptions and an effect size to be detected of 0.35 with 90% power and a two-sided alpha of 0.05, a sample size of $N=412$ ($N_1=206$, $N_2=206$) is required.

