where, Y_{ik} are the SDQ scores; SDQ_BL_{ik} are the baseline SDQ scores; TX_{ik} is the treatment/control variable indicator; $Local_authority_{ik}$ are indicator of local authority (strata, 6 groups: Cambridge, Peterborough, Wirral, Birmingham, London Borough Merton, Gloucestershire); μ_{0k} is the random intercept term for family and r_{ik} is the individual level variation.

We will use simple coding for the contrast of local authority, so that our intercept retains the grand mean and nominally use Birmingham as our reference level.

Distributional assumptions for the primary linear model will be checked and alternative methods are listed in section “assumption checking”.

If insufficient random effect variance is found, we will reduce the model to a linear regression with cluster robust standard errors (Green & Vavreck, 2008). The alternative primary analysis would be specified as follows:

$$Y_i = \beta_0 + \beta_1 SDQ_BL_i + \beta_2 local_authority_i + \beta_3 TX_i + r_i, \quad r_i \sim N(0, \sigma^2)$$

Secondary outcomes analysis

Secondary outcomes will be analysed following the same method as the primary outcome. However, the distributions of these secondary outcomes will be assessed prior to conducting the analysis, if range restriction is present or a binary outcome (out of home placement), we will consider using a generalized linear mixed model (GLMM) instead (Poisson or logistic respectively). All measures have scores that are integer numbers and positive scores, so the Poisson distribution under this condition is completely acceptable if needed. The GLMM is denoted as follows:

$$L1: g(Y_{ik}) = \beta_{0k} + \beta_{1k} SDQ_BL_{ik} + \beta_{2k} local_authority_{ik} + r_{ik}, \quad r_{ik} \sim N(0, \sigma^2)$$

$$L2: \beta_{0k} = \gamma_{00} + \gamma_{02} TX_k + \mu_{0k}, \quad \mu_{0k} \sim N(0, \tau_2^2)$$

$$\beta_{1k} = \gamma_{10}$$

Note: $g(.) = \log_e(.)$, where $g(.)$ is the log link function for the secondary outcome measures for example, if a count model was more appropriate for the scores, whereas the primary outcome, $g(Y_i) = Y_i$.

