2. Homogeneity of variance – variance of the residuals across groups is the same. There is scope to fit models allowing for heterogeneous groups, but the setup is different (Generalized linear mixed model - GLMM).
3. Residuals are approximately normally distributed – plotting QQ plot

Alternative methods if distributional assumptions not met

If distributional assumptions are not satisfied, as appropriate, a generalized linear mixed model with alternate link function will be used. Alternatively, data transformation could be used but use of the GLMM is preferable.

Sensitivity analyses

- Exploring the impact of missing data on trial outcomes by investigating likely missing data mechanisms and re-fitting the primary outcome within a multiple imputation framework (including exploring MAR and MNAR mechanisms via delta-based controlled multiple imputation);
- Adding practitioner as a source of clustering in the model. The primary analysis will be rerun including a third level where individual parent will be nested in family and families will be nested by practitioner. An additional random intercept will be included to account for practitioner level clustering at level 3 as follows:

$$L1: Y_{ijk} = \beta_{0jk} + \beta_{1jk}SDQ_BL_{ijk} + \beta_{2jk}local_authority_{ijk} + r_{ijk}, \quad r_{ijk} \sim N(0, \sigma^2)$$

$$L2: \beta_{0jk} = \gamma_{00k} + \gamma_{20k}TX_k + \mu_{0jk}, \quad \mu_{0jk} \sim N(0, \tau_{00}^2)$$

$$\beta_{1jk} = \gamma_{10k}$$

$$L3: \gamma_{00k} = \delta_{000} + U_{0k}, \quad U_{0k} \sim N(0, \varphi_{00}^2)$$

$$\gamma_{10k} = \delta_{100}$$

where, Y_{ijk} are the SDQ scores; SDQ_BL_{ijk} are the baseline SDQ scores; TX_{ijk} is the treatment/control variable indicator; $Local_authority_{ijk}$ are indicator of local authority (strata, 6 groups: Cambridge, Peterborough, Wirral, Birmingham, London Borough Merton, Gloucestershire); μ_{0jk} is the random intercept term for family, U_{0k} is the random intercept term for practitioner, and r_{ik} is the individual level variation.

- Exploring the impact of different levels of intervention receipt on outcomes. We will use two-stage least squares instrumental variables regression to examine the effect of the intervention in those who receive varying levels of it.

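### The residual-check fallback can move the primary result off the mean-difference scale on which the trial was sized, and it conflicts with the SAP's own identity link for the primary outcome

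*SAP*

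**What the plan says.** The SAP's *Primary analysis (6 month)* section specifies a linear mixed model with baseline SDQ score, local authority and a random family intercept. Its treatment effect is an adjusted mean difference in SDQ externalising score, which is then standardised as Hedges' g. The same section adds: "Distributional assumptions for the primary linear model will be checked and alternative methods are listed in section" headed *Assumption checking*. That section lists three checks: residuals against predictors, equal residual variance and a QQ plot. None has a threshold. The consequence, under *Alternative methods if distributional assumptions not met*, is: "If distributional assumptions are not satisfied, as appropriate, a generalized linear mixed model with alternate link function will be used". A transformation is allowed as a less preferred option.

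The protocol, under *Analysis of primary and secondary outcomes*, applies the same checks to all analyses and gives the same fallback, there as a GLM.

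Other text points the other way. The note after the GLMM formula in the SAP's *Secondary outcomes analysis* sets the log link against the primary outcome, for which the link is the identity. The only model labelled as an alternative primary analysis is a linear regression with cluster-robust standard errors, used when family-level variance is insufficient. That model still gives a mean difference.

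Both documents size the trial on the mean-difference scale: "an effect size to be detected of 0.35 with 90% power and a two-sided alpha of 0.05", where d = 0.35 "equates approximately to a 2-point change on our primary outcome". They add that a smaller effect is unlikely to be meaningful.

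**The concern.** Residuals exist only once the model has been fitted to the 6-month outcomes. Under the fallback, the link function, and with it the effect measure, therefore depends on the outcome data. That a switch may occur is pre-specified. The trigger, the distribution, the link and the transformation are not, and the choice between GLMM and transformation is only a stated preference. Two careful analysts could follow this SAP and report primary results on different scales.

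What is at stake is the reading of the trial. The clinical threshold is in points, and the sample size and Hedges' g assume a difference in means. A log-link coefficient or a difference on a transformed scale is a different quantity, and neither document gives it a target or a rule for returning to points.

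**Working it through.** **1. The sample size belongs to the mean difference.** Inputs, from *Sample size* in the SAP (the protocol agrees): d = 0.35, power 90%, two-sided alpha 0.05, baseline correlation 0.5, "so also allow for an ICC=0.5", "an average cluster size within families of up to a maximum of 1.5 parents", and "20% of families being lost to follow-up at the 12-month post-randomisation follow-up time point".

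- Per arm, unadjusted: 2 × ((1.960 + 1.282)/0.35)² = 171.5, so 172 (t-test version 173).
- Baseline adjustment: 1 − 0.5² = 0.75. Design effect: 1 + (1.5 − 1) × 0.5 = 1.25.
- Normal version: 172 × 0.75 × 1.25 = 161.25; divided by 0.8 this is 201.6, so 202 per arm and 404 in total.
- The t version gives 406. Rounded up to whole families it gives 137 families per arm, 274 families and 411 parents.

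The stated 412 is therefore reproduced closely, as a sample size for a difference in means. At 412 with 20% loss, power for that difference is about 90.7%.

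**2. What 2 points becomes on a log link.** The implied SD is 2/0.35 = 5.7 on a 0–20 score. The documents give no control mean m, so the values below are assumptions. The rate ratio is (m − 2)/m.

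| Assumed control mean | 6 | 8 | 10 | 12 | 14 |
|---|---|---|---|---|---|
| Rate ratio for a 2-point fall | 0.67 | 0.75 | 0.80 | 0.83 | 0.86 |

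No single ratio corresponds to the stated threshold.

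**3. Does the switch help or harm inference?** Simulation: 220 analysed families (275 × 0.8) with one or two parents each, latent ICC 0.5 and baseline correlation 0.5, scores rounded and bounded at 0–20, 2000 trials per scenario. A linear model and a Poisson log-link model were fitted, both with family-clustered standard errors, as stand-ins for the mixed models. A Shapiro–Wilk test at 5% stands in for the unspecified trigger. Monte Carlo standard error at 5% is √(0.05 × 0.95/2000) = 0.5 percentage points.

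No treatment effect, % of trials:

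| Score shape | Linear, type I | Poisson, type I | Switch rule, type I | Smaller of the two p-values, type I | Normality rejected |
|---|---|---|---|---|---|
| Near normal | 4.80 | 4.45 | 4.75 | 5.00 | 27.7 |
| Strong right skew | 4.40 | 5.10 | 5.10 | 5.45 | 100 |
| Ceiling | 5.15 | 5.20 | 5.20 | 5.30 | 99.95 |

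Latent effect of 0.35 SD:

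| Score shape | Linear, power % | Poisson, power % | Mean difference | Rate ratio |
|---|---|---|---|---|
| Near normal | 87.55 | 87.30 | −1.82 | 0.82 |
| Strong right skew | 85.00 | 83.95 | −1.34 | 0.72 |
| Ceiling | 86.00 | 86.00 | −1.59 | 0.89 |

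The two models disagreed on significance in 0.3% to 2.9% of trials across the six settings. The last two columns show the change of effect measure: the right-skewed scenario has the smallest difference in points and the strongest rate ratio.

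**The case against.** The strongest reply is that the SAP already fixes the scale. It gives the primary outcome the identity link, its named alternative primary model is linear, and it assigns odds and rate ratios to categorical, count or binary outcomes. On that reading a ratio as the primary result is only an inference. This stands in part: the documents nowhere say outright that the primary result will be a ratio. But the identity-link note is an aside to the secondary-outcome formula. It does not say that the link holds when the checks fail, and it cannot be squared with a fallback that the primary section itself invokes.

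A second reply is blinding. Both documents say that the analysing statistician is blind, which limits a choice driven by the result. This also stands in part. The SAP's *Roles and responsibilities* gives the Trial Statistician's role as Research Fellow/Trial Manager, while the protocol's *Blinding* section says that the Trial Manager is not blind. Even a fully blinded switch changes the effect measure.

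A reader might infer three stronger things, and none is supported:

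- *The switch inflates the 5% error rate.* Even taking the smaller of the two p-values gave 5.0% to 5.5%.
- *A switch is almost certain on a bounded score.* The SAP asks only for approximate normality. A formal test rejected in about 28% of near-normal trials and in nearly all skewed or ceiling trials, and the documents do not say which shape to expect.
- *A log-link result could not be judged against 2 points.* Fitted means can be converted to a difference in points. The plan just does not say that they will be, or how.

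**Conclusion.** The concern holds as a point about the estimand. The plan allows the primary linear model to be replaced after thresholdless visual checks, and this conflicts with its own identity link. The replacement would not directly deliver the mean difference on which the sample size, the 2-point threshold and Hedges' g depend. The error rate is not materially at risk, and the switch gains no validity either: the linear model with family-clustered standard errors held 4.4% to 5.2% under skewed and ceiling scores.

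This rests on assumed score shapes, a Poisson model as the alternative link, a formal test in place of visual inspection, and clustered standard errors in place of random effects. Transformed models and other links were not simulated. How often the switch would occur is unknown.

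**What to change.** In the SAP's *Primary analysis (6 month)* section, state that the identity-link adjusted mean difference is the primary estimate whatever the residual plots show. Specify family-level cluster-robust standard errors in advance; tying them to the plots would leave the inference dependent on the same checks. The SAP already names such standard errors for its low-variance fallback, which can stay because it keeps the scale. Move any GLMM or transformed model of the primary outcome to *Sensitivity analyses*, with its distribution and link named. Limit the alternative-methods text accordingly, and align the matching text in the protocol's *Analysis of primary and secondary outcomes*. Reconcile the Trial Statistician's role with the blinding statement at the same time.

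The cost is wording in two documents; the sample size stays at 412. The downside is a possible slight loss of efficiency if residuals are strongly skewed. None appeared against the Poisson model in the scenarios above, but other models were not tried.

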We will also consider in a sensitivity analysis the role of Triple P practitioner as an additional source of clustering. As practitioners will deliver the intervention to several families allocated to the intervention arm only, this will be a form of partial nesting and may lead to an underestimation of standard errors (and thus inflated Type-I error) if not appropriately accounted for. To account for any clustering, we will fit a heteroscedastic partially nested mixed-effects model. We will also report intra-cluster correlation coefficients, the number of clusters, and cluster sizes.

Secondary outcomes will be analysed similarly. However, secondary outcomes that are adolescent self-report will use linear regression to compare mean scores between trial arms, controlling for baseline scores, age, sex, and local authority. No random effects are included when analysing these outcomes as we do not need to adjust for parent clustering of responses, i.e. there is no dependency of responses from within the same household as we only anticipate one adolescent per household to respond.

We will explore the extent to which there were differential intervention effects by local authority by extending our primary analysis model to include sub-group by trial arm interaction

terms. Similarly, potential moderators, young person learning disability status, ethnicity, and in-care vs in family home status, will be explored by inclusion of an interaction of moderator and treatment allocation variables into the primary analysis model. In addition to interpreting the magnitude and statistical significance of interactions, plots of the interactions will also be examined. These analyses will be hypothesis generating in nature only (i.e., will not be confirmatory and only indicate whether further research targeting the intervention may be warranted).

We will conduct two further sensitivity analyses:

- Exploring the impact of missing data on trial outcomes by investigating likely missing data mechanisms and re-fitting the primary outcome within a multiple imputation framework (including exploring MAR and MNAR mechanisms via delta-based controlled multiple imputation);

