Fidelity: The fidelity score is the average proportion of sessions content delivered. Fidelity items will be scored 0, 0.5, and 1. Total fidelity session score will be dependent on the session and will range between 20 and 30. This is based on agreed progression criteria and Triple P guidance on minimum number of sessions required in their opinion as the intervention developer.

Adherence: Number of sessions attended (Progression criteria: green= \geq 75% of families attend at least the first 8 of the 10 sessions; amber= 50-74%; red= $<$ 50%). The proportion of sessions attended out of a maximum of ten will be the instrumental variable in this analysis.

For both fidelity and adherence, a Two Stage Least Square approach will be used to estimate the model and Huber-White standard errors reported which are robust to clustering. The R packages ‘ivpack’ and ‘ivreg’ will be used to implement the two-stage instrumental variable analysis (Jiang & Small, 2014; Fox Kleiber, & Zeileis, 2021). Compliance (session adherence) will be instrumented by the intervention allocation (Angrist & Imbens, 1995). However, robust SE will be reported instead of including random effects in to the model. The stage 1 model is defined as follows:

$$Compliance_k = \beta_0 + \beta_1 TX_k + \varepsilon_{jk}$$

Predicted values for, $Compliance_k$, from the stage 1 model will be included in the stage 2 model, as follows:

$$Y_{ik} = \beta_0 + \beta_1 \widehat{compliance}_k + \beta_2 baseline_{ik} + \beta_3 Local_authority_k + \beta_4 \widehat{compliance}_k \cdot Local_authority_k + r_{ik}$$

Subgroup analyses

In addition to the primary and secondary outcomes, we have considered that the following outcomes may moderate the primary outcome of this trial.

- Ethnicity,
- In-care vs family home status: all instances of out of home placement will be recorded at each follow-up time point. This will include the reason for and duration of out of home placement.
- Learning disabilities (LD): Children and young people will be invited to complete two subtests of the Wechsler Abbreviated Scale of Intelligence-II (WASI-II; Wechsler, 2011) to index their Verbal IQ. This scale is to be administered with a researcher (face-to-face, telephone, videoconferencing). The two subsets are to be included are Vocabulary and Similarities.

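### The SAP's adherence analysis contradicts itself on the instrument and includes an interaction it cannot identify, and its practitioner model departs from the protocol's partially nested one

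*SAP*

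**What the plan says.** **Adherence and fidelity (SAP, Sensitivity analyses).** Under Adherence, the SAP writes "The proportion of sessions attended out of a maximum of ten will be the instrumental variable in this analysis". The next paragraph says "Compliance (session adherence) will be instrumented by the intervention allocation". Two equations follow:

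- Stage 1 regresses compliance on an intercept and the arm indicator TX, and nothing else.
- Stage 2 regresses the outcome on predicted compliance, baseline, local authority, and predicted compliance by local authority.

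Random effects are dropped from this analysis, with "Huber-White standard errors reported which are robust to clustering".

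**Practitioner clustering.** The Protocol (Analysis of primary and secondary outcomes) explains that practitioners deliver to families in the intervention arm only, calls this partial nesting, and commits: "we will fit a heteroscedastic partially nested mixed-effects model". The SAP instead specifies three levels in which "families will be nested by practitioner". Its equation has a practitioner random intercept that is not multiplied by TX and a single residual variance. It does not say which practitioner, if any, an SAU family is assigned to, and its version history does not explain the departure.

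**The concern.** An instrument has to be independent of the confounders of exposure and outcome. Allocation is, by randomisation. Attendance is chosen after randomisation by the families whose outcomes are being measured, so it is the exposure. An analyst holding this SAP is told both things.

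The interaction raises a different problem. Each endogenous term in stage 2 needs its own source of exogenous variation. Compliance by local authority is endogenous for the same reason that compliance is, and no instrument is supplied for it. The analyst must either change the specification or run the stages by hand. The second route can produce differences between authorities that only reflect differences in attendance.

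For practitioners, the purpose is to test whether clustering in one arm alters the primary standard error. A model that is silent on the arm without that clustering leaves the answer to a coding decision made at analysis.

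**Working it through.** **The plan's own figure.** The point disputes no number, but the inputs can be checked against the stated sample size. The SAP (Sample size) plans for "an effect size to be detected of 0.35 with 90% power and a two-sided alpha of 0.05", with "an average cluster size within families of up to a maximum of 1.5 parents" and, for correlation within families, "so also allow for an ICC=0.5". It also assumes a baseline to follow-up correlation of 0.5 and 20% loss.

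- Individually randomised: 172 per arm.
- Design effect: 1 + (1.5 − 1) × 0.5 = 1.25.
- Baseline adjustment: 1 − 0.5² = 0.75.
- 172 × 1.25 × 0.75 / 0.80 = 201.6, so 202 per arm and 404 in total, against the stated 412. Power at 206 per arm with 20% loss is 0.907.

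The sample size reproduces and nothing below changes it.

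**Identification of stage 2.** There are six local authorities, hence five contrasts.

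- Parameters: intercept 1 + compliance 1 + baseline 1 + authority 5 + interaction 5 = 13.
- Instrument columns with allocation as sole excluded instrument: intercept 1 + TX 1 + baseline 1 + authority 5 = 8.
- Endogenous terms: 1 + 5 = 6, against 1 excluded instrument.

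Since 8 is less than 13, a single 2SLS call cannot estimate the model. Adding TX by local authority supplies 5 more columns, giving 13, which is exactly identified.

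**Running the stages by hand.** With stage 1 containing TX only, predicted compliance takes one value per arm. Each authority's slope is then its own intention-to-treat effect divided by overall attendance. Assume, for illustration, a true effect of full attendance of 1.0 everywhere, six equal-sized authorities, no attendance in SAU, and attendance of 40% in one, 80% in another and 60% in four. Overall attendance is (0.4 + 0.8 + 4 × 0.6) / 6 = 0.6.

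| Attendance | Intention-to-treat effect | Reported slope | True |
|---|---|---|---|
| 40% | 0.4 | 0.4 / 0.6 = 0.67 | 1.0 |
| 80% | 0.8 | 0.8 / 0.6 = 1.33 | 1.0 |
| 60% | 0.6 | 0.6 / 0.6 = 1.00 | 1.0 |

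The second-stage standard errors are also uncorrected, because the residuals are computed from predicted and not actual compliance.

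**Simulation of the main effect.** 400,000 families; assumed mean attendance about 0.75, attendance confounded with outcome, true effect 0.35 / 0.75 = 0.467.

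| Specification | Estimate |
|---|---|
| Attendance as its own instrument (equivalent to ordinary regression) | 0.58 |
| Allocation as instrument, covariates in both stages, no interaction | 0.468 to 0.472 |
| Hand-run, TX-only stage 1, no interaction | 0.468 to 0.472 |
| Hand-run as written, simple coding of authority | 0.468 to 0.473 |
| Hand-run as written, dummy coding, attendance varying from 0.50 to 0.95 by authority | 0.335 or 0.586, by reference authority |

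**Practitioner model.** Simulation under no treatment effect: 110 analysed families per arm (137 × 0.8 ≈ 110), family and residual variances 0.5 each, 150 replicates per scenario. Practitioner variances and the 5 families per practitioner are assumptions. The 1.14 is 137 intervention families over the 120 practitioners in the Protocol's Timeline. Entries from the third column on are mean standard errors.

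| Families per practitioner; practitioner variance | Empirical SD | Partially nested | SAP model, SAU families as singletons | SAP model, all SAU families in one cluster |
|---|---|---|---|---|
| 5; 0.05 | 0.130 | 0.136 | 0.135 | 0.262 |
| 5; 0.10 | 0.138 | 0.143 | 0.141 | 0.335 |
| 1.14; 0.05 | 0.128 | 0.127 | 0.128 | 0.261 |

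The last column is inflated because one undivided practitioner variance stays in the control mean. In the first row the two-level standard error is 0.127, and √(0.127² + 0.05) = 0.257, close to the simulated 0.262. Type I error there was 0.007 (Monte Carlo error about 2 percentage points).

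**The case against.** Several stronger readings are tempting, and the documents do not support them.

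- **That the adherence analysis is an as-treated comparison.** A reader could infer this from the sentence naming attendance as the instrument. The next paragraph and the only stage 1 equation both use allocation. It is a contradiction to remove.
- **That leaving covariates out of stage 1 biases the estimate.** Under randomisation it does not: without the interaction the hand-run estimate matches the fully specified one (0.468 to 0.472 for both).
- **That the main effect is wrong.** The SAP states simple coding of local authority for the primary model. Under that coding the main effect in the illustration is (0.67 + 1.33 + 4 × 1.0) / 6 = 1.0, which is correct. Distortion needs dummy coding. The coding is not restated for the instrumental-variable analysis.
- **That the standard errors are too small.** If they ignored families, a design effect of 1.25 would make them 1 − 1/√1.25 = 11% too small. But the SAP says they are robust to clustering and offers them in place of random effects, and it names cluster-robust errors as the fallback for the primary model. Family clustering is the evident intent; only the cluster variable is unstated.
- **That the practitioner model is necessarily wrong.** Coding SAU families as singletons nearly reproduces the partially nested result. The Protocol's contamination paragraph also says that different practitioners serve each condition, so SAU families might have their own, although neither document describes recording who they are. At about 1.1 families per practitioner the true effect is probably small.

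What survives is the contradictory sentence, the uninstrumented interaction, and the unexplained, under-specified departure from the protocol's practitioner model.

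**Conclusion.** The point holds, limited to two sensitivity analyses. The adherence model cannot be fitted by 2SLS as written (13 parameters, 8 instrument columns). Run by hand, it creates differences between authorities whenever attendance varies: 0.67 to 1.33 around a uniform 1.0 under the assumed attendance rates. The main effect is distorted only if local authority is dummy coded.

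The practitioner model conflicts with the Protocol and leaves the SAU coding open. Under the assumed variances, that choice moves the standard error from nearly identical to the partially nested value to about twice it (0.262 / 0.136 = 1.9; 0.335 / 0.143 = 2.3; 0.261 / 0.127 = 2.1).

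Attendance rates, strength of confounding and practitioner variances are illustrative; the count of parameters against instruments needs only the SAP's equations and its six authorities. The primary estimate, sample size, power and alpha do not change.

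**What to change.** In the SAP, before analysis:

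1. Delete the sentence naming attendance as the instrument. State that randomised arm is the instrument and that the exposure is the proportion of ten sessions attended, set to 0 in SAU. The zero needs saying because the SAP's Presentation of adherence also refers to SAU sessions.
2. Put baseline SDQ and local authority in both stages and fit the model in one 2SLS call.
3. Drop compliance by local authority, or add TX by local authority as instruments.
4. Say that the robust standard errors are clustered on family. This clarifies the existing wording.
5. Restore the Protocol's practitioner model: a practitioner random effect multiplied by TX, arm-specific residual variance, and a stated coding for SAU families.

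The cost is a few sentences of SAP text and a few lines of code. No new data are needed.
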